1 PROTOCOL SYNOPSIS

Title:	An uncontrolled, single centre, healthy volunteer, Phase II proof-of-concept trial investigating MR-enterography (MRE) image quality of Lumentin® 44, a new egg albumen based oral small bowel filling contrast agent.
Short title:	Lumentin MR-enterography PoC trial in healthy volunteers
EudraCT Code:	2022-002193-84
Phase of development	Phase II
Background & study rationale	
Lumentin® 44 is being developed as a novel oral contrast medium to be used in diagnostic examinations of the abdomen. Phase II studies have been performed using computed tomography (CT) assessment with encouraging results. If the same product can also be used in Magnetic Resonance-enterography (MRE) it could be an advantage for a radiological department to only handle a single oral contrast medium for both modalities, CT and MRI. In addition, administration of Lumentin® 44 has shown few side effects and may be a more tolerable alternative to the oral media used today in CT and MRI. The current study aims to explore if the signal characteristics of Lumentin® 44 is favourable in MRE.
 
This proof-of-concept (PoC) trial is performed in healthy volunteers (HVs) with the aim to show that Lumentin® 44 can be used as an oral small bowel filling contrast agent for MRE.

Primary objective	
 To evaluate if Lumentin® 44 used as a bowel filling agent in MRE examination generates images with acceptable diagnostic quality.
Secondary objectives	
 To evaluate plasma electrolytes including, potassium, sodium, phosphate, and calcium, as well as ionized calcium concentration levels during 24 hours after intake of Lumentin® 44. To evaluate bowel filling properties (extension and distension) of Lumentin® 44. To evaluate the safety and tolerability of Lumentin® 44 intake.

Primary outcome	
 Visual evaluation of the MRE images from each trial subject with respect to motility, artefacts, mucosal evaluation and overall diagnostic impression.
Secondary outcomes	
 Concentration of plasma electrolytes including, potassium, sodium, phosphate, and calcium, as well as ionized calcium in blood samples taken at T0h, T1h, T2h, T4h, T6h, T8h, and T24h. Bowel filling properties (extension and distension) in each of 5 selected sub-segments of the small bowel. Any treatment emergent adverse events (TEAEs) and treatment emergent adverse drug reactions (TEADRs).
Investigational product, formulation, dosage and mode of administration:	
Lumentin® 44 Powder for oral foam provided in labelled white sachets white sachets containing 17.4 g powder. Potable water (commercially available still water 0.5 L per bottle) for the preparation of the foam will be used.
 
Lumentin® 44 powder for oral foam will be delivered from APL to the clinical site, by order via the hospital pharmacy and stored temporarily at the site. The investigational product (Lumentin® 44 foam) is then prepared in-situ by adding 0.5 L potable water to Lumentin® 44 powder contained in one sachet, and the blend is then mixed to a stable foam in a dedicated preparation unit. The freshly prepared foam will be administered to the patient within 5 to 10 minutes. The in-situ preparation will follow a procedure attached to the clinical trial protocol. The staff responsible for the in-situ preparation will be trained using the procedure and their training documented in the Trial Master File. Two sachets (0.9 L foam per sachet) will be required per subject.

Trial design	
This is an uncontrolled, single centre phase II trial. Enrolled HVs (n=10) will undergo gadolinium (Gd) based MRE after oral intake of Lumentin® 44.
 
Interested HVs will be identified primarily among medical students at the medical hospitals at Malmö and Lund. Posters will be placed at the departments and invitation letters will be handed out.
 
HVs interested in participating will be invited to attend a pre-screening visit where their suitability based on age and health status will be assessed. Fifteen HVs who fulfil the pre-screening criteria and are still interested in participating will be asked to attend a screening visit at the clinic and if

	
eligible for the trial they will then visit the clinic for MRE assessment within 1-2 weeks.
 
Only the first 10 of the eligible HVs will be asked to come for MRE examination and the remaining eligible subjects will be asked to stand by in case any of the 10 subjects are unable to come or cannot undergo the examination.
 
HVs will be asked to fast for 6 hours prior to the examination on the day of the MRE examination. Clear liquid in small volumes up to 2 decilitres is allowed. Prior to MRE, Lumentin® 44 will be provided to them in volumes of up to 1.5 L and at least 1.1 L of Lumentin® 44 must be drunk. The subjects will be asked to drink the solutions of oral contrast agent within 45 minutes to 1 hour.
 
Subjects not able to drink at least 1.1 L of Lumentin® 44 will be withdrawn from the trial.
 
Prior to the intake of Lumentin® 44, an intravenous (IV) antecubital cannula will be placed and used for blood sampling and administration of Gd contrast agent during the MRE assessment.

Assessments	
Screening assessments: HVs fulfilling the eligibility criteria and who sign the consent to participate will undergo a physical examination, perform a pregnancy test (females only) and have a creatinine blood sample taken. Medical history, demographics, concomitant treatment and illnesses will also be recorded..
 
MRE assessment: MRE will start within 10 minutes after the contrast agent has been drunk and will last for approximately 40 minutes.
 
The HV will be brought to the MRE-scanner suite inside the magnet using the moving table and scanning will commence. All series will be taken as per standard clinical MRE protocol recognised by radiologists in Europe and North America. After dynamic series acquisition, a spasmolytic agent will be given and 3D gradient-echo series will be taken and will be repeated 40 seconds thereafter, following IV administration of Gd contrast agent at a dose of 0.1 mmol/kg per body weight. Subsequently, the remaining series will be taken according to protocol.

	
Electrolyte assessment: A blood (baseline) sample for electrolyte analysis will be collected just prior to the HV starting to drink Lumentin® 44. A second blood samples will be collected one hour after the baseline blood sample. No more Lumentin® 44 can be drunk after this blood sample has been collected. Additional blood samples will be collected at 2, 4, 6, 8, and 24 hours post baseline samples.
 
Safety assessment: The occurrence of adverse events and concomitant treatment will be recorded for the duration of the trial.
 
For safety reasons, subjects will be contacted within 2 to 4 days after the MRE examination by the investigator and asked about occurrence of any adverse event. No other follow-up is planned.

Trial population	HVs fulfilling the eligibility (in-/exclusion) criteria.
Number of subjects	A total of ten fully evaluable HVs will be included in the trial.
Inclusion criteria	
 1. Healthy volunteers of either gender at least 18 years at the time of signing the informed consent. 2. Females must either present a negative pregnancy test or be surgically sterile (hysterectomy or tubal ligation) or postmenopausal (i.e., experienced 12 consecutive months without menstruation). 3. Following verbal and written information about the trial, the subject must provide signed and dated informed consent before any trial related activity is carried out.
Exclusion criteria	
 1. Glomerular Filtration rate (GFR) below 60 ml/min/1.73 sqm body surface. All subjects will have a plasma creatinine taken at screening for calculation of estimated GFR (eGFR). 2. History of drug related reaction to gadolinium contrast agents. 3. Have had gadolinium injection during the last 4 weeks. 4. Claustrophobia not coping with MRE examination. 5. Metal objects and medical devices in the body not judged by the investigator to be compatible with MRE. 6. Hypersensitivity to Buscopan® (Butylhyoscopin). 7. Having swallowing difficulties. 8. Known allergy to egg albumen.

	
9. Known sensitivity to any of the components of the investigational product.10. Clinical suspicion of ongoing disease by the investigator.11. Being, in the opinion of the investigator, unlikely to comply with the clinical trial protocol.12. Previously included in this trial.13. Participating in or having participated in another clinical trial within the last 4 weeks.
Statistical analyses	
All subjects who have completed the trial will be included in the statistical evaluation.
 
No statistical tests will be conducted. Confidence intervals may be constructed and will then be 2-sided and of 95% confidence.
 
Continuous data will be summarised using descriptive statistics (N, mean, median, standard deviation, minimum and maximum). Categorical data will be summarised by frequency tables (numbers and percentages).
 
Unless otherwise stated, all analyses will be done on observed cases without any substitution of missing values.

Schedule of Assessments

Visit/Contact	1	2	3	4	5
	Pre-screening	Screening	MRE examination	Blood sampling	F-U ⁽¹⁾ and early termination
Day	-21 to -1	0	14	15	Visit 2 +2 days
Visit window (days)			+/- 7 days	-	+ 2
Subject information	X	X			
In/exclusion criteria	(X) ⁽²⁾	X			
Informed consent		X			
Physical examination		X			
Pregnancy test ⁽³⁾		X			
Creatinine blood sample		X			
Subject demographics (incl. height and weight)		X			
Concomitant treatment	X	X	X	X	X
Concomitant illnesses	X	X			
Medical history	X	X			
Adverse event(s) recording			X ⁽⁴⁾	X	X
Placement of IV antecubital cannula			X ⁽⁵⁾		

Visit/Contact	1	2	3	4	5
	Pre-screening	Screening	MRE examination	Blood sampling	F-U ⁽¹⁾ and early termination
Day	-21 to -1	0	14	15	Visit 2 +2 days
Visit window (days)			+/- 7 days	-	+ 2
MRE Scan			X		
Dispensing of Lumentin® 44			X		
Administration of Gd contrast (6)			X		
Administration of Buscopan® (6)			X		
Evaluation of extension and distension of bowel filling agents			X		
Blood sampling			X ⁽⁵⁾ (pre-, 1, 2, 4, 6, 8h)	X (24h)	
Compliance			X		

- 1) Subjects will be contacted by telephone two to four working days post MRE assessment.
- 2) Only some of the criteria will be checked including, inclusion criterion 1 and exclusion criteria 2, 3, 4, 5, 6, 7, 8, 12 and 13.
- 3) Urine pregnancy test of all females who are not surgically sterile (hysterectomy or tubal ligation) or postmenopausal (i.e., experienced 12 consecutive months without menstruation).
- 4) Telephone interviews will be conducted 2 days after MRE assessment to investigate if any AEs occurred during the first days after the imaging procedure
- 5) An IV antecubital cannula will be placed for pre-blood samples and used during the first 8h including administration of gadolinium during the MRE procedure. Thereafter it will be discarded. Blood sampling on the following day (24h time point) will be drawn without a cannula.
- 6) Gadolinium (Gd) and Buscopan® will only be administered as part of the MRE examination.

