8.3 Subject Withdrawal and Replacement

8.3.1 *Withdrawal from Trial Therapy*

Subjects must be withdrawn if the intake of the contrast agent has to be stopped, please see section 9.2 Dosage and Administration.

8.3.2 *Withdrawal from Study*

Subjects may withdraw from the trial at any time and for any reason without prejudice to his or her future medical care.

Subjects must be withdrawn under the following circumstances:

- The subject withdraws consent
- Subjects who have not fasted (clear water allowed) for at least six hours prior to the intake of the contrast agent
- The subject is unable to drink at least 1.1 L of Lumentin® 44
- The subject is unable to complete the MRE examination, due to e.g., claustrophobia.
- Violation of eligibility criteria

Subjects withdrawn due to the above circumstances will be replaced by one of the five remaining eligible HV subjects on standby after screening.

Subjects may be required to withdraw after discussion with the Sponsor and/or Investigator for the following reasons:

- AEs
- Use of prohibited medication (see Section 10)
- At the discretion of the Investigator

In all cases, the reason(s) for withdrawal must be recorded on the Case Report Form (CRF). If a subject is prematurely withdrawn from the trial for any reason, the Investigator must make every effort to perform the evaluations described for the Early Termination Visit (see Section **Fel! Hittar inte referenskälla.**).

If a subject has withdrawn informed consent and still agrees to attend the Early Termination Visit, this will be documented on the CRF.

For subjects who are withdrawn after they receive the trial drug, the Early Termination page will be completed in the CRF.

HVs withdrawn prior or during the MRE examination (i.e., no evaluable MRE scan has been generated) will be replaced by a new HV. HVs withdrawn after the completion of MRE examination and NOT fulfilling the mandatory criteria for withdrawal listed above will not be replaced.

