9.2 Dosage and Administration

The Investigational products will be taken orally by the subject during a period of 30 minutes - 1 hour.

A volume of 1.1 L to 1.5 L shall be consumed. A steady intake rate of the contrast agent is recommended to guarantee fullness of the gastrointestinal tract from stomach to terminal ileum of the small bowel.

The intake of the contrast agent will be stopped in case of an AE occurs or if the subject is unable to consume more than 1.1 L within 1 and ½ hour. The subject will be withdrawn in case the intake of the contrast agent has to be stopped.

The subject will be withdrawn from the trial if the maximum volume of the Investigational product taken by the subject is less than 1.1 L.

There is no risk of overdose.

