11.2.7 MRE examination

Preparation before MRE: Subjects will be fasting (2 decilitres of clear water is allowed) for at least six hours prior to the MRE procedure.

The MRE-examination will take approximately 40 minutes. The MR-examination will not be performed if the subject has not been able to drink at least 1.1 L of Lumentin® 44.

Broadly, MRE is a scanning technique for creating detailed images of parts of the human body, using a strong magnetic field and radio waves. It is based on the magnetisation properties of atomic nuclei. A powerful, uniform, external magnetic field is employed to align the protons that are normally randomly oriented within the water nuclei of the body part examined. This alignment (or magnetisation) is disrupted by introduction of an

external Radio Frequency (RF) wave energy. The nuclei return to their resting alignment through various relaxation processes and in doing so emit RF energy. Tissues are characterised by two different relaxation times, of which T1, the longitudinal relaxation time, determines the rate at which excited protons return to equilibrium. It is a measure of the time taken for spinning protons to realign with the external magnetic field. The contrast and brightness of the image are predominately determined by T1 properties of tissue.

During an MRE-examination, the subject will be asked to lie prone on a movable table that will slide into a doughnut-shaped, deep opening and centred for scanning the small bowel. As part of the procedure a strong magnetic field will be generated around the subject, and pulsating radio waves will be directed at the body. Because of loud thumping and tapping noises during the scan the subject will be given headphones to listen to music or earplugs to help block the sound. The subject will be able to communicate with the technician who gives instructions during the test. The contrast agent Clariscan® (0.1 mmol/kg) and the muscle relaxant Buscopan® (40 mg) (to reduce bowel motility) will be administered IV. Clariscan and Buscopan can be replaced with comparable product according to the standardised procedures at the clinic. The specific details of the MRE-system used will be noted in the CRF.

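### The synopsis ends intake at the one-hour blood sample while section 9.2 sets its volume-based stop at 1½ hours, which by implication treats a slow drinker in two different ways

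*Combined protocol and SAP*

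**What the plan says.** **Synopsis, Electrolyte assessment.** The baseline sample is taken just before drinking starts. Then: "A second blood samples will be collected one hour after the baseline blood sample". The next sentence reads "No more Lumentin® 44 can be drunk after this blood sample has been collected". This bar on further drinking appears nowhere else; 7.1, 9.2 and 11.2.6 do not repeat it.

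**Section 9.2.** Intake is stopped if an adverse event occurs, or if the subject is "unable to consume more than 1.1 L within 1 and ½ hour". The consequence is the same for both: "The subject will be withdrawn in case the intake of the contrast agent has to be stopped". Section 8.3.1 makes this mandatory by cross-reference: "Subjects must be withdrawn if the intake of the contrast agent has to be stopped, please see section 9.2 Dosage and Administration".

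**The volume minimum.** The synopsis says "Subjects not able to drink at least 1.1 L of Lumentin® 44 will be withdrawn from the trial", and 7.1 agrees. Section 8.3.2 lists as a mandatory withdrawal reason "The subject is unable to drink at least 1.1 L of Lumentin® 44", 9.2 has an equivalent sentence, and 11.2.7 adds "The MR-examination will not be performed if the subject has not been able to drink at least 1.1 L of Lumentin® 44". None of these statements carries a time limit.

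**The intake period.** The synopsis and 7.1 give 45 minutes to 1 hour; 9.2 gives 30 minutes to 1 hour.

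**Sampling.** Section 11.2.6 sets T1h at one hour, without a window and without mentioning whether drinking must have ended.

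**The concern.** Two limits govern the same act. If nothing may be drunk after about 60 minutes, a rule that allows 90 minutes to pass 1.1 L has no function. If the 90-minute rule is meant to operate, the bar in the synopsis cannot hold as written.

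Three things depend on which limit the site follows:

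- **Withdrawal and replacement.** Under 8.3.2 a subject who cannot reach 1.1 L is withdrawn and replaced from the standby subjects.
- **The analysis set.** Section 13.3 analyses the subjects who fulfilled the trial, so the same slow drinker may be in or out.
- **The meaning of T1h.** Under the synopsis no intake follows the T1h sample. Under 9.2 the sample may be drawn with part of the volume still to be drunk. Electrolyte change is a secondary objective, and 7.3.2 gives the electrolyte investigation as one reason for the narrower volume range with a higher lower limit.

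Site staff are likely to look to 9.2 for dosing and 11.2.6 for sampling. Neither section carries the bar, so the synopsis could be breached unnoticed.

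**Working it through.** The plan states no figure that could be reproduced here; the check is a comparison of the rules on one time axis.

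**1. Clock.** T0h is the baseline sample, just before the first sip. T1h is T0h + 60 min. The documents do not say when the 1½ hours in 9.2 begin; I assume at the start of drinking, taken as about T0h.

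**2. The two limits.** Synopsis: no intake after T1h, about 60 min. Section 9.2, volume criterion: 90 min. Gap: 90 − 60 = 30 min.

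**3. A subject below 1.1 L at 60 min, with no adverse event.**

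| Question | Synopsis | Section 9.2 |
|---|---|---|
| Must drinking stop at 60 min? | Yes | Volume limit not yet reached |
| Can 1.1 L still be reached? | No | Possibly, up to 90 min |
| Withdrawn and replaced? | Yes, by combining the bar with the 1.1 L minimum | Not yet |
| T1h relative to intake | After it | Possibly during it |

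**4. Who falls between the limits.** All the stated intake periods end at 1 hour. A subject who reaches 1.1 L within the hour and then stops is treated alike by both texts. The difference arises only for those who overrun, and these are the subjects whom a 1½-hour limit addresses.

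**5. Illustration only.** Assume a steady rate, which 9.2 recommends, and the clock in step 1. Reaching 1100 mL by 60 min needs 1100/60 = 18.3 mL/min; by 90 min it needs 1100/90 = 12.2 mL/min. Between these rates the outcomes differ. At the lower rate the volume at 60 min is 1100 × 60/90 = 733 mL, which is 1100 − 733 = 367 mL short of the minimum. The rate band depends on the assumed start and steady rate, and says nothing about how many subjects would lie in it.

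**6. Number affected.** Section 7.3.2 reports an average of 1026 mL drunk by 73 subjects in earlier trials. That is a total volume, after a request for 0.75 to 1.5 L, with no standard deviation and no drinking time. It cannot be read as a volume at 60 min, so no share of subjects can be computed.

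**The case against.** The strongest reply is that the texts can be obeyed together. Section 9.2 says when intake must stop; it nowhere states that a subject may drink beyond one hour, and its opening sentence places intake within the hour. A site that stops everyone at the T1h sample breaks neither rule, and the 1½-hour clause is then redundant. This stands in part: there is a way to comply with both. But it leaves the 90-minute limit without function, and a reader of 9.2 alone would not know of the bar.

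The reply also corrects two tempting readings. A reader might infer that 9.2 withdraws only at 1½ hours. It does not: an adverse event stops intake and leads to withdrawal at any time, and 9.2 separately withdraws anyone whose maximum volume is below 1.1 L, with no time attached. A reader might also infer that the synopsis itself orders withdrawal at one hour. It does not mention withdrawal in that sentence; the result follows only when the bar is combined with the 1.1 L minimum.

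Finally, the consequences are limited. Withdrawn subjects are replaced, enrolment continues to ten evaluable subjects (16.5.1), no tests are planned (13.1), and a clean-file meeting also decides on exclusions (13.5). T1h is one of seven sampling times and keeps its nominal definition. All of this stands and bears on weight. It does not settle which rule the site should follow.

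**Conclusion.** The inconsistency is real and nothing else in the protocol resolves it. Its size is 60 against 90 minutes. For a subject who overruns the planned period and is below 1.1 L at one hour, the two texts imply different answers on withdrawal, replacement and inclusion in the analysis, and on whether T1h is taken during or after intake. The comparison assumes that the 1½ hours run from about the start of drinking.

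The documents do not support going further. The number of subjects affected is unknown. Nor can one infer a bias in the image scores: under either text no scan is done below 1.1 L, and no direction or size of effect can be stated. The point should be corrected before the trial starts, but it does not call the design into question.

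**What to change.** The sponsor and investigator should reconcile the synopsis (Trial design and Electrolyte assessment), 7.1 and 9.2 so that they state one intake period, in place of the present 45 minutes to 1 hour and 30 minutes to 1 hour, and one latest intake time. The T1h text in 11.2.6 should then be made consistent with that time, so that it is clear whether the sample is meant to follow the end of intake. Which limit applies is for them to decide.

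The cost is wording in four places. No samples, visits or subjects are added.

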4 LIST OF ABBREVIATIONS AND DEFINITIONS OF TERMS

Abd-CT	Abdominal Computerised tomography
ADR	Adverse Drug Reaction
AE	Adverse Event
ATC	Anatomical Therapeutic Chemical
ASI	Additional Safety Information
b.w.	Body weight
CD	Crohn's Disease
CI	Confidence Interval
CRF	Case Report Form
CT	Computerised Tomography
CTE	Computerised Tomography - enterography
CRO	Clinical Research Organization
DMF	Drug Master File
DRL	Drug Reference List
EC	European Community
EEA	European Economic Area
EMA	European Medicines Agency
EU	European Union
EWP	Egg White Protein (also referred to as egg albumen)
FA	Full Analysis
GCP	Good Clinical Practice
Gd	Gd Gadolinium
(e)GFR	(estimated) Glomerular Filtration Rate
GI	Gastrointestinal
GRAS	Generally Recognized as Safe
HU	Hounsfield Units
HVs	Healthy Volunteers
IB	Investigator Brochure
ICH	International Council for Harmonisation of Technical Requirements for Pharmaceuticals for Human Use
IEC	Independent Ethics Committee
IMP	Investigational Medicinal Product
IP	Investigational Product

IV	Intravenous
MRE	Magnetic Resonance - enterography
MRI	Magnetic Resonance Imaging
MedDRA	Medical Dictionary for Regulatory Activities
Ph. Eur.	European Pharmacopeia
PoC	Proof of Concept
RCDAS	Radiological Crohn's disease Activity Score
RCE	Relative Contrast Enhancement
RF	Radio Frequency
ROI	Region of Interest
SAE	Serious Adverse Event
SAP	Statistical Analysis Plan
STD	Standard Deviation
SDV	Source Data Verification
SUSAR	Serious Unexpected Suspected Adverse Reactions
TEAE	Treatment-Emergent Adverse Event
TEADR	Treatment-Emergent Adverse Drug Reaction
TMF	Trial Master File
V/V	Volume per volume
W/W	Weight per weight
WHO	World Health Organisation

